### **Project summary:**

Policemen recruited in the Chandigarh police who take care of the safety of VIPs most likely suffer from chronic stress, as they need to be vigilant round the clock. Since chronic stress has been shown to be responsible for multiple molecular changes at both the genomic and epigenomic levels, it can lead to various diseases like hypertension, diabetes and even cancer. Further, it has been shown that deregulation in DNA Damage Response (DDR) and DNA repair pathways is responsible for cancer. Though it is well known that yoga relieves stress and anxiety, literature lacks in studies that focus onto assessing the effect of yoga on DDR and DNA repair pathways at the molecular level. In the present study, we propose to investigate the role of yoga in modulating DDR and repair. For this, personnel of Chandigarh police who need to be extra vigilant could be the ideal cohorts. A sample size of around 230 security guards from Chandigarh police shall be recruited in the study with their consent, upon screening them for mild or severe stress on Cohen's Perceived Stress scale. 10 ml of blood will be withdrawn from the participants followed by separation of serum, plasma and WBCs from these subjects. Biochemical assays to measure the levels of cortisol (stress marker) will be performed and analyzed. This study proposes to analyze DDR markers like  $\gamma$ H2AX, 53BP1, and ATM and the extent of damage in WBCs using comet and DNA repair assays. Post the baseline assessments, they will undergo Yoga intervention for a period of 3 months, and at the end of three months, they will be assessed again on the same parameters. The baseline and post intervention results will be compared for discussion and conclusion. This study will help us to understand the effect of yoga in maintaining genomic integrity and stability at the molecular level and can assist the Department of Chandigarh police in designing strategies to improve the overall well being of policemen.

**Key words:** Yoga exercises, DNA damage response (DDR), DNA double-strand break (DSB), DNA double-strand break repair (DSBR), Cancer

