#### Key questions expected to be answered by this study:

- a) What are the effects of yoga on biochemical and molecular markers of stress leading to changes in DNA damage response
- b) Is there any change in the DNA repair capacity of yoga-practicing subjects as compared to matched controls?
- c) What will be the mechanism by which yoga modulates DNA damage response and repair.

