### Methodology

Recruitment of individuals: Department of Police, Chandigarh has agreed to help us on this aspect. Policemen working for Chandigarh Police will be chosen based on the inclusion and exclusion criteria.

Subjects: Those security guards (age: >20 and <60) who are willing to consent to participate in this study will be screened for moderate and higher stress on Cohen's PSS, according to inclusion criteria and randomly divided between Intervention (Yoga Group) and Control Group.

Sample Size: The sample size of 206 was calculated for 99% confidence level (reliability coefficient = 2.58), at the alpha level of 0.05, a power of 0.95, and a relative precision of 0.2, derived from a pilot study done on breast cancer patients and yoga practitioners (Ram et al, 2013). Assuming a 10% drop out rate, a total of 229 subjects will be recruited.

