### **Design of the study**

In a randomized control trial (RCT), participants are allocated randomly between intervention and control groups to compare the treatments, which enables statistical control over the influences imparted by the aforementioned treatments. In the present study, the policemen who satisfy our eligibility criteria and willing to consent to participate in our study will be enrolled, grouped randomly in intervention and control groups, and assessed for the dependent variables of the study before and after the Integrated Yoga intervention period.

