### **Variables**

- Socio-demographic details – age, diet, alcohol consumption, etc.
- Evaluation of stress level on Cohen's Perceived Stress Scale (pre and post intervention) (Cohen, Kamarck & Mermelstein, 1983)
- Evaluation of stress level using vital parameters: Blood pressure and resting heart rate of participants will be recorded pre and post intervention.

- Evaluation of stress level using molecular parameters: (pre and post intervention) 10 ml of blood will be withdrawn from the subjects by trained phlebotomists, and coded. WBCs and plasma will be separated using standard protocols and stored at -80°C. Plasma will be utilized to assess the levels of cortisol.
- Assessment of chromosomal translocations: (pre and post intervention) Genomic DNA will be extracted from WBCs isolated, and tested for chromosomal translocations using PCR assay. Isolated genomic DNA will be subjected to nested PCR using primers specifically designed to check for t(14;18) and t(11;14) translocations.
- Assessment of DDR and DNA repair:
- *Immunofluorescence*: Isolated PBMCs will be subjected to DDR analysis by immunofluorescence. For this, these cells will be fixed and stained with various DDR markers like γH2AX, 53BP1, pATM.
- *Gene expression analysis*: Total RNA will be isolated from these cells; cDNA will be synthesized and the expression of following DDR and DNA repair genes will be performed using real-time PCR: RAD51, MRE11, RAD50, NBS1, KU70, LIGASE IV, PARP1
- *Comet assay*: Cells will be used to perform both the neutral as well as alkaline comet assay to assess for the number of single- and double-strand breaks.
- Telomeric length: Relative telomere length (TL) using quantitative polymerase chain reaction (qPCR) will be performed on genomic DNA isolated from control and group blood samples and will be compared.

Time Line for experiments:

S.No.	Experiments	Time point
1.	Cortisol levels	0 day
2.	DDR: Immunofluorescence for γH2AX, 53BP1, and ATM.  Gene expression analysis for KU70, LIGASE IV, RAD51,	0 day

	PARP1, MRE11, RAD50, NBS1	
3.	Nested PCR for Chromosomal Translocations	0 day
4.	DNA repair: Comet assay	0 day
5.	Cortisol levels	3 months
6.	DDR: Immunofluorescence for $\gamma$ H2AX, 53BP1, and ATM.  Gene expression analysis for KU70, LIGASE IV, RAD51,  PARP1, MRE11, RAD50, NBS1	3 months
7.	Nested PCR for Chromosomal Translocations	3 months
8.	DNA repair: Comet assay	3 months

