Date: February 29, 2020

NCT number: Not

Available

Official Project Title

Investigating the Role of Yoga in Alleviating
Chromosomal Translocations in Security Guards
of Chandigarh Police Who Are Responsible for
the Safety of VIPs

Statistical Analysis Plan (SAP)

1. Introduction

This Statistical Analysis Plan (SAP) outlines the planned analyses for the study titled “Investigating the Role of Yoga in Alleviating Chromosomal Translocations in Security Guards of Chandigarh Police Who Are Responsible for the Safety of VIPs”. It defines the methods for analyzing study endpoints, including descriptive, inferential, and correlation analyses.

2. Objectives and Endpoints

1. Analysis of molecular markers related to DNA damage response and repair before and after the practice of yoga on Chandigarh Police.
2. To examine the molecular mechanism by which yoga may modulate DNA damage response and repair.

3. Analysis Populations

- **Full Analysis Set (FAS):** All participants meeting eligibility criteria and providing baseline and outcome data.
- **Per-Protocol Set (PPS):** Subset of participants completing the study without major protocol deviations.

4. General Statistical Considerations

- All analyses will be conducted using **GraphPad Prism v8.0.2** and **JASP v0.19.3**.
- Two-sided significance level of $\alpha = 0.05$ will be applied.

- Adjusted p-values from post hoc tests will also use the **0.05 threshold** for significance.
- Continuous variables will be summarized with **mean \pm SD** (if normally distributed) or **median with interquartile range** (if non-normal).
- Categorical variables will be summarized as **frequencies and percentages**.

5. Assessment of Assumptions

- **Normality:** Assessed using the **Shapiro-Wilk test**.
- **Homogeneity of variance (ANOVA assumption):** Checked using **Levene's test**.

6. Statistical Methods

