6.1 Comparisons of Two Groups

- **Normally distributed data:** Student's *t*-test (paired or unpaired as appropriate).
- **Non-normal data:** Wilcoxon matched-pairs signed rank test (paired) or Mann-Whitney test (independent).

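### The trial is randomised, but nothing readable makes yoga versus control the deciding analysis; the stated conclusion and Objective 1 are before versus after, and SAP 6.1 leaves the choice open

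*Protocol*

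**What the plan says.** **Design.** The Protocol (Methodology, Subjects) has eligible guards "randomly divided between Intervention (Yoga Group) and Control Group". Its Design section describes a randomised trial as one where "participants are allocated randomly between intervention and control groups to compare the treatments", then says of this study only that both groups are assessed before and after the intervention period.

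**Basis of the conclusion.** The Project summary says: "The baseline and post intervention results will be compared for discussion and conclusion". The summary mentions no control group; as written, all recruited participants go on to yoga.

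**Objective.** Objective 1 has the same wording in the Protocol and in SAP section 2: "Analysis of molecular markers related to DNA damage response and repair before and after the practice of yoga on Chandigarh Police". The SAP names no primary endpoint and no contrast.

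**Tests.** SAP 6.1 offers Student's t-test, "paired or unpaired as appropriate", for normal data, and the signed-rank or Mann-Whitney test otherwise. Neither form is tied to an endpoint or a question.

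**Mentions of the control group.** Key question (b) asks: "Is there any change in the DNA repair capacity of yoga-practicing subjects as compared to matched controls". The telomere entry under Variables says the assay "will be performed on genomic DNA isolated from control and group blood samples and will be compared". SAP 6.2 mentions comparison with a control group, but as a post hoc test for more than two groups. SAP section 9 promises effect sizes and 95% confidence intervals without saying of which contrast.

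**The concern.** Randomisation protects one comparison: yoga against control. A paired test within the yoga arm discards that protection. It attributes to yoga anything that moved between day 0 and 3 months: a change over time common to all guards, a shift in assay conditions, or regression to the mean.

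Regression to the mean acts directly on the Perceived Stress Scale (PSS), because guards enter only if they score above 15. It reaches the molecular markers only through their correlation with PSS. An assay shift is possible but not documented. The Time schedule places assays during the yoga period, while the Variables section stores white cells and plasma frozen, so a guard's two samples could be run together for some assays.

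Followed as written, the plan would allow a significant pre/post change in the yoga arm, or a result significant in yoga but not in control, to be reported as a yoga effect when there is none. It would also allow the choice of contrast to be made after the results are seen.

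**Working it through.** **1. The plan's own figure.** 206/(1 − 0.10) = 228.9, which gives the stated 229. The 206 cannot be checked, because no mean, SD, proportion or effect size is given. The point here does not depend on it.

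**2. Common inputs.** From the documents: 206 evaluable guards, two-sided 0.05 (SAP section 4), PSS entry above 15. Assumed: equal allocation, so 206/2 = 103 per arm; no yoga effect; all SDs, correlations and shifts below.

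**3. Shift shared by both arms.** Let s be the shift in SDs of the marker and r the pre/post correlation. The standardised mean change is dz = s/√(2(1 − r)), and the paired test has noncentrality dz·√103. For r = 0.5 and s = 0.2, dz = 0.2 and the noncentrality is 0.2 × 10.15 = 2.03, giving 52% significant. The arms are independent, so the chance that yoga is significant and control is not is p(1 − p); here 0.52 × 0.48 = 25%.

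| r | Paired test in yoga arm significant, s = 0.1 / 0.2 / 0.3 | Yoga significant, control not |
|---|---|---|
| 0.3 | 14 / 40 / 72% | 12 / 24 / 20% |
| 0.5 | 17 / 52 / 85% | 14 / 25 / 12% |
| 0.7 | 26 / 74 / 97% | 19 / 19 / 3% |

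With s = 0 both are about 5%. Simulation (20,000 trials per setting) agrees. In it, between-arm tests of the 3-month value, the change and the baseline-adjusted value reject in 4.7–5.4% of trials.

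**4. Regression to the mean in PSS.** Assume a bivariate normal score with SD 6. With c = (15 − mean)/6 and λ = φ(c)/(1 − Φ(c)), the expected fall is (1 − r)·6·λ points. At mean 15, λ = 0.798, so r = 0.5 gives 0.5 × 6 × 0.798 = 2.4 points with no treatment effect. Simulated rates at which the paired test is significant:

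| Population mean | r = 0.5 | 0.6 | 0.7 | 0.8 |
|---|---|---|---|---|
| 13 | 100% | 99.9% | 99% | 92% |
| 15 | 99% | 97% | 91% | 74% |
| 17 | 90% | 82% | 69% | 49% |
| 20 | 47% | 38% | 30% | 21% |
| 23 | 15% | 14% | 11% | 9% |
| 25 | 8% | 8% | 7% | 6% |

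Between-arm tests reject in 4.5–5.4%. The Protocol's research review describes policemen as chronically stressed, so the higher means are at least as plausible as the lower.

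**5. Regression to the mean in markers.** Let ρ be the marker's correlation with baseline PSS and k the fraction of it that persists at 3 months. The expected change is (1 − k)·ρ·λ SDs. At mean 15, ρ = 0.3 and k = 0.7 this is 0.3 × 0.3 × 0.798 = 0.07 SD. Rejection rates at ρ = 0.3, for marker r = 0.5 and 0.7:

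| Mean | k = 0.5 | k = 0.7 | k = 0.9 |
|---|---|---|---|
| 15 | 23%, 35% | 11%, 15% | 6%, 6% |
| 20 | 9%, 10% | 6%, 7% | not run |

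With ρ = 0, or at mean 25, the rate is about 5%. For markers this mechanism is therefore small in most settings.

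**6. Precision of the between-arm test.** At the Protocol's 95% power and 103 per arm, the unadjusted detectable difference is 0.505 SD. Adjustment for baseline multiplies it by √(1 − r²), giving 0.48, 0.44 and 0.36 SD at r = 0.3, 0.5 and 0.7.

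**The case against.** The strongest reply is that the harm is permitted, not planned. SAP 6.1 is a generic menu that includes the valid unpaired test. The Design section says why one randomises, key question (b) asks a control-group question, and SAP section 9 commits to CONSORT reporting. A before/after objective can be read as comparing change between arms. The Project summary is not an analysis rule, and it reads as if the trial had one arm.

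Much of this is fair as description. The claim is that the deciding contrast is never designated, not that control comparisons are never mentioned. The work-plan figure and Flow Chart 3 are not readable, so it covers the readable text only. But none of these passages settles the matter. Key question (b) concerns DNA repair capacity alone. The telomere line covers one variable and gives no time point or test. SAP 6.2 applies to more than two groups, and this trial has two. CONSORT is named as a reporting standard and is not turned into a contrast. That the summary omits the control arm is a further conflict with Methodology and makes the case for rewording it stronger.

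Two objections on size stand. Every magnitude rests on assumed inputs, and the largest concern PSS, which neither objective names, at the lower population means. The near-5% error of the between-arm test also assumes intact randomised groups. The exclusion of non-compliers from the yoga arm only, and a full analysis set that requires outcome data, could disturb that.

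**Conclusion.** The concern holds. The one stated basis for the conclusion and Objective 1 are before/after, and SAP 6.1 lets a within-arm paired test carry the inference in a randomised trial. Confidence in this gap is high.

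The size is conditional. With no shift and no regression to the mean, the paired test keeps its 5%. For the Objective 1 markers, a modest shared shift of 0.1–0.3 SD raises it to 14–97% over r = 0.3 to 0.7. For PSS, selection at entry alone gives anything from 6% to 100%, depending mainly on how far the population mean lies above the cut-off.

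This must be settled before outcome data are examined, because it decides which comparison supports the trial's claim. That applies only to naming the contrast. Baseline adjustment improves precision and is not needed for validity.

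**What to change.** **SAP 6.1, add:** *For each continuous marker measured at 0 and 3 months, and for PSS, inference is the yoga-versus-control difference at 3 months, with its 95% confidence interval. Within-arm paired tests are descriptive and do not support efficacy claims.*

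**Project summary and Objective 1 (Protocol and SAP section 2):** reword to the change in the yoga group compared with the control group.

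**Recommended, not required:** estimate that difference by ANCOVA on the marker's own baseline value. Fix the scale (raw, log or rank) for each marker in the SAP before outcome data are examined.

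**What this does not cover:** the choice of a primary endpoint, translocation results recorded as present or absent, multiplicity across markers, the exclusion of non-compliers from the yoga arm only, the full analysis set definition, and complete-case analysis. Each needs its own resolution.

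**Cost:** a few sentences and slightly different analysis code. No new participants, samples or assays.

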## **Introduction:**

### **Origin of the proposal**

It is well known that yoga relieves stress and anxiety. Since chronic stress has been shown to be responsible for multiple molecular changes at both the genomic and epigenomic levels, that can lead to various diseases like hypertension, diabetes and even cancer. Alterations in DNA damage response (DDR) and repair are considered as one of the major causative agents of cancer. As the effects of yoga on DNA damage response (DDR) and DNA repair are not known, studying the role of yoga will provide us with an insight on the role of yoga in modulating DDR in a way that can alleviate the effects of chronic stress on DDR and repair leading to cancer. DDR is a signaling event, which is activated upon DNA damage and encompasses DNA damage repair, cell-cycle checkpoint activation, apoptosis and senescence. Deregulation in DDR has been known to be responsible for carcinogenesis and it has been suggested that defects in DNA repair is the hallmark of most cancers (Gavande, 2016). Although preliminary studies have reported the effects of yoga in relieving oxidative stress, but no study has investigated the effects of common yoga practice on DDR and DNA repair. This study proposes to analyze the effect of yoga on DDR markers like  $\gamma$ H2AX, 53BP1, and ATM and the extent of damage in WBCs using comet and DNA repair assays. Such analysis will uncover the effect of yoga on DDR and cell survival mechanisms. We will also estimate the extent of oxidative free radicals as well as other DNA repair machinery. We will further evaluate the possible mechanisms by which yoga affects DDR and DNA repair by studying the expression and activation of DDR proteins upon DNA damage. Hence, this study is designed to examine the effect of yoga on DDR and DNA repair and the associated molecular mechanisms. This data could be useful to not only examine the cancer preventive role of yoga but also could be extended to potentiate the therapeutic efficacy of commonly used anti-cancer drugs.

### **Stress at Molecular Level**

Stress can induce responses commonly associated with infections and tissue damage and increase the levels of various biomarkers of inflammation (Black, 2002). Several

studies have reported stress induced immune dysfunction as it was found that receptors for stress neuropeptides and hormones are broadly expressed in immune cells (Glaser & Kiecolt-Glaser, 2005). The presence of long-term stress, anxiety and depression is a prelude to increased biological susceptibility to various psychiatric ailments, physical health problems as well as an increased risk of various chronic diseases like diabetes, hypertension and even life threatening diseases like cancers (Miller, Chen & Parker, 2011; Antonova, Aronson & Mueller, 2011; Fleshner & Klotz, 1998; Mariotti, 2015). According to a study, psychological stress induces oxidative damage to nuclear DNA (Moreno-Villanueva et al., 2018). Another study done in year 2000 showed involvement of psychological stress in the pathogenesis of cancer via oxidative DNA damage in rats (Irie et al., 2000), whereas a recent study concluded that stress mediated DNA damage plays an important role in the pathogenesis and development of breast cancer (Yasuda, Sakakibara & Shimoi, 2017). A study done on human population indicated that cells from the stressed population were more sensitive to the induction of DNA damage and had higher level of residual damage (Dimitroglou et al., 2003). Triggering curiosity further, a study demonstrated in detail, how stress promotes prostate carcinogenesis in mice, in an adrenaline-dependent manner by evading apoptosis (Hassan et al., 2013), and another study showed that psychological stress can induce oxidative stress and is a well-known causative agent for cancer (Hayashi, 2015).

### **Yoga And DNA Damage**

A growing interest has been seen, among the cancer survivors, in the use of various complementary therapies as adjuvants to conventional treatment in the anticipation of coping with the treatment (Buettner et al., 2006). A number of studies including randomized trials have reported positive therapeutic outcomes following yoga programs. This includes reported improvements in blood pressure, immune function and serum cortisol levels (Henderson & Donatelle, 2004). Banerjee et al. reported that integrated approach of yoga intervention modulates the stress and DNA damage levels in breast cancer patients during radiotherapy (Banerjee et al., 2007). Scientists today are driven towards understanding the mechanisms by which yoga and meditation achieve relaxation of mind and body, and its effects on various physiological processes and

oxidative stress (Chong, Tsunaka & Chan, 2011; Dhawan et al., 2018). It has been shown that yoga based lifestyle intervention not only reduces oxidative DNA damage, but also improves the integrity of sperm DNA and reduces mutation load (Dhawan et al., 2018). Though these studies describe the beneficial and biochemical aspects of yoga, the effects of yoga at the molecular level on DNA damage response and repair, deregulation in these processes leading to cancer still needs to be determined.

### **Yoga in Ancient Texts**

Ancient texts talk about two kinds of diseases in accordance with the site where disease manifests: Physical and mental. The assessment of components of the physical body (doṣa, dhātu, mala, agni, etc.) and the treatment thereafter is covered by Ayurveda, whereas, assessment of the mind is covered by Yoga.

According to caraka, both body and mind are the locations of disorders as well as pleasures. Good health and pleasurable life are maintained and bestowed by balanced use of application of time, intelligence, whereas diseases occur by negative and excessive utilization of time, intelligence and sense objects. Thus, abnormalities in lifestyle may contribute to both psychic and somatic disorders.

According to suśruta sūtra 24.08, psychic diseases are thought to originate from aggravation of the rājasa and tamasa guṇa, while physical diseases originate from aggravation of vāta, pitta and kapha doṣa.

On the other hand, Yoga broadly divided diseases into two categories: ādhijāvyādhi and anādhijāvyādhi. ādhijāvyādhi are the diseases that originate at the mind level, or psychosomatic, whereas, anādhijāvyādhi are the diseases, which do not originate at the mind level. anādhijāvyādhi may include infections and contagious diseases, which may be handled through conventional medicine, i.e., modern medicine, Ayurveda, etc. ādhijāvyādhi, however, is caused due to agitation at the mind level during one's interaction with the world around. These agitations cause violent fluctuations in the flow of prana (vital energy) within the nāḍī (energy channels). These disturbances at the

prāṇa level manifests into tridoṣa imbalance. Imbalance in tridoṣa disturb the metabolic activities of the body, consequently forming āma (metabolic waste), which further obstructs the srota (channels in the body). This obstruction, ultimately, manifests as disease at the physical level.

